11.1.4 Assessment of relationship of AE to treatment

The possibility that the adverse event is related to study agent will be classified as one of the following: not related, unlikely, possible, probable, definite.

11.1.5 Follow-up of AEs

All AEs, including lab abnormalities that in the opinion of the investigator are clinically significant, will be followed according to good medical practices and documented as such.

11.1.6 Reporting Deviations

A protocol deviation is any noted variance or difference in the conduct of the study from the written protocol plan. All deviations will be reported by completing the DCP Deviation Reporting form available on the CPN website: <https://cancerpr.ipower.com/member/Deviations.shtml>

The deviation reporting form will be completed in Word format and submitted by email to the DCP medical monitor (see Section 11.2.2.2 for contact information).

11.2 Serious Adverse Events

11.2.1 DEFINITION: Fed. Reg. 75, Sept. 29, 2010 defines SAEs as those events, occurring at any dose, which meet any of the following criteria:

- Results in death
- Is life threatening (*Note: the term life-threatening refers to an event in which the patient was at risk of death at the time of the event; it does not refer to an event which hypothetically might have caused death if it were more severe*).
- Requires inpatient hospitalization or prolongation of existing hospitalization
- Results in persistent or significant incapacity or substantial disruption of the ability to conduct normal life functions
- Is a congenital abnormality/birth defect
- Important medical events that may not result in death, be life-threatening or require hospitalization may be considered serious when, based upon appropriate medical judgment, they may jeopardize the patient or subject and may require medical or surgical intervention to prevent one of the outcomes listed.

11.2.2 Reporting SAEs to DCP

11.2.2.1 The Lead Organization and all Participating Organizations will report SAEs on the DCP SAE form found at http://prevention.cancer.gov/files/clinical-trials/SAE_form.doc.

11.2.2.2 Contact the DCP Medical Monitor by phone within 24 hours of knowledge of the event.

[name] [name], FACS
National Institutes of Health, National Cancer Institute
Division of Cancer Prevention
[name]
[name]
[contact]
Fax (with cover sheet, Attn: Dr. [name]): [contact]
Email (preferred): [contact]

Include the following information when calling the Medical Monitor:

- Date and time of the SAE
- Date and time of the SAE report
- Name of reporter
- Call back phone number
- Affiliation/Institution conducting the study
- DCP protocol number
- Title of protocol
- Description of the SAE, including attribution to drug and expectedness

11.2.2.3 The Lead Organization and all Participating Organizations will FAX or email written SAE reports to the DCP Medical Monitor within 48 hours of learning of the event using the paper SAE form.

The written SAE reports will also be FAX'ed or emailed to [name], Study Principal Investigator and CCS Associates, DCP's Regulatory Contractor.

[name].
Email: [contact]
[contact]

DCP's Regulatory Contractor, CCS Associates:
Email: [contact]
[contact]

Participating Sites will also FAX this form to the CPN Operations Office within 48 hours of learning of the event at [contact]. See the Data Management Plan (see CPN web site) sections "Data Collection" and "Data Entry and Processing" for further instructions as SAEs must also be recorded on the participant's appropriate case report forms.

11.2.2.4 The DCP Medical Monitor and regulatory staff will determine which SAEs require FDA submission, per CFR 21 Section 312.32

11.2.2.5 The Lead Organization and all Participating Organizations will comply with applicable regulatory requirements related to reporting SAEs to the IRB/IEC.

11.2.3 Follow-up of SAE

Site staff should send follow-up reports as requested when additional information is available. Additional information should be entered on the DCP SAE form in the appropriate format. Follow-up information should be sent to DCP as soon as available. SAEs that are determined to be at least possibly related to study intervention will be followed according to institutional standards of care until resolved.

12. STUDY MONITORING

12.1 Data Management

The Mayo Clinic Cancer Center database will be the database of record for the protocol and subject to NCI and FDA audit. Minimum Data Sets will be submitted to DCP per contract requirements. Please see 2012 CPN Master Data Management Plan.

12.2 Case Report Forms

Participant data will be collected using protocol-specific case report forms (CRF) utilizing NCI-approved Common Data Elements (CDEs). The approved CRFs will be used to create the electronic CRF (e-CRF) screens for data entry into the Mayo Clinic Cancer Center database. Amended CRFs will be submitted to the DCP Protocol Information Office for review and approval.

12.3 Source Documents

A source document is any document, form, or record where *specific participants'* data are first recorded. FDA [21 CFR 312.62 (b)] requires that the investigator "...prepare and maintain accurate case histories

designed to record all observations and other data pertinent to the investigation on each individual treated with the investigational agent or employed as a control in the investigation.” Among many other items, source documents include:

- Inpatient and outpatient medical records
- Progress notes
- Consults
- Nursing notes
- Pathology reports
- Radiology reports
- Medicine/radiation administration records
- Surgical reports
- Laboratory reports
- Admission forms
- Flow sheets that are signed and dated
- Protocol or study road maps
- Appointment books
- Participant diaries/calendars
- Participant-completed symptom diary
- Participant-completed Vaccine Report Card.

12.4 Data and Safety Monitoring Plan

The Master DSMP, applicable to all studies within the CPN Consortium provides detailed information regarding data and safety monitoring for this study. The trial will be monitored closely for occurrence of adverse events by the study team and by the Mayo Clinic Cancer Center Data Safety Monitoring Board (DSMB). The DSMB will be consulted regarding whether or not accrual should be suspended to allow for investigation in the occurrence of severe adverse events, particularly for those that are possibly, probably, or definitely related to the study agent.

12.5 Sponsor or FDA Monitoring

The NCI, DCP (or their designee), pharmaceutical collaborator (or their designee), or FDA may monitor/audit various aspects of the study. These monitors will be given access to facilities, databases, supplies and records to review and verify data pertinent to the study.

12.6 Record Retention

Clinical records for all participants, including CRFs, all source documentation (containing evidence to study eligibility, history and physical findings, laboratory data, results of consultations, etc.), as well as IRB records and other regulatory documentation will be retained by the Investigator in a secure storage facility in compliance with Health Insurance Portability and Accountability Act (HIPAA), Office of Human Research Protections (OHRP), Food and Drug Administration (FDA) regulations and guidances, and NCI/DCP requirements, unless the standard at the site is more stringent. The records for all studies performed under an IND will be maintained, at a minimum, for two years after the approval of a New Drug Application (NDA). For NCI/DCP, records will be retained for at least three years after the completion of the research. NCI will be notified prior to the planned destruction of any materials. The

records should be accessible for inspection and copying by authorized persons of the Food and Drug Administration. If the study is done outside of the United States, applicable regulatory requirements for the specific country participating in the study also apply.

12.7 Cooperative Research and Development Agreement (CRADA)/Clinical Trials Agreement (CTA)

A CRADA/CTA agreement is not needed as, the contact between DCP and Mayo along with the Mayo subcontract with the University of Pittsburgh delineate each party's responsibilities.

13. STATISTICAL CONSIDERATIONS

13.1 Study Design/Description

This is a randomized Phase II double blind placebo controlled trial designed to assess the effects of the MUC1-1 peptide with poly-ILC adjuvant vs. placebo. There will be 3 "Parts" to the study to allow periodic monitoring and the opportunity to evaluate whether to proceed after each part. The key endpoints from each part are listed below:

Part I: The ratio of the week 12 to week 0 IgG levels will be calculated and compared between the MUC1 vaccine and placebo (primary endpoint, see 13.4).

Part II: Assessment of the booster response at week 55 vs. week 52 (T55/T52) for the vaccine as compared to placebo (key secondary endpoint, see 13.5)

Part III: Comparison of the adenoma recurrence rate from surveillance exams occurring at least one year and up to three years after Week 0 vaccine administration – MUC1 peptide versus placebo. All patients will be followed for this endpoint (key secondary endpoint, see 13.5)

In addition to these key powered endpoints for the 3 different parts, we will also assess the following additional secondary endpoints:

- Comparison of adverse events between the MUC1 vaccine and placebo during part 1 and 2 (13.7).
- To assess patient –reported vaccine-related side effects from the Vaccine Report Card.
- Comparison of the proportion of patients with at least a 2-fold increase in the IgG ratio between the 2 arms at 12 weeks (13.5).
- Comparison of the adenoma recurrence rates between MUC1 and placebo by excluding the following types of adenomas. These adenomas are excluded since they may represent missed or residual adenomas from the baseline exam. These analyses are exploratory.
 - Participants with adenomas ≤ 5 mm,
 - Participants with adenomatous tissue which may represent residual adenoma at the site of the previous advanced adenoma,
 - Participants with adenomatous tissue detected in the same segment of the bowel as the previous advanced adenoma.
- Assessment of participant-reported injection site reaction events from the Vaccine Report Card (Appendix E).

In addition, we will assess the following translational endpoints (see 13.10):

- To compare the anti-MUC1 antibody titer at the time of surveillance colonoscopy for the purpose of evaluating the anti-MUC1 antibody response in relation to adenoma recurrence. Since surveillance colonoscopy is generally at 3 years after an advanced adenoma, this titer will typically be obtained at approximately week 156.
- To evaluate MUC1 expression on baseline advanced adenomas and on recurrent adenomas detected at surveillance colonoscopy. Based on current knowledge of MUC1 expression and function in tumor cells, MUC1 negative adenomas are not expected to grow as immune escape variants, but this has never been tested before and the trial will provide an appropriate setting to study this issue.
- To evaluate levels of circulating myeloid derived suppressor cells (MDSC) in the vaccinated and the placebo group and correlate with anti-MUC1 antibody levels and adenoma recurrence.
- To establish a biospecimen repository archive including live cells, plasma, and germline DNA for future immunologic and other assays, for testing not currently accommodated within the budget of this trial.

There are limited Quality of Life (QOL) data on participants who participate in chemoprevention trials and we intend to create a databank of QOL information by administering the “Was It Worth It” (WIWI) questionnaire at trial completion across multiple trials. We will seek to evaluate participant perception of their experience in trial participation once we have a reasonable amount of information (large enough sample size). Since participants who participate in these chemoprevention trials are high risk but otherwise healthy, the WIWI tool would help answer simple questions about participants’ assessment of whether or not participation in this trial was “worth it.”

In addition to the WIWI Questionnaire, participants will be asked to complete a pre-vaccine questionnaire at baseline (prior to the Week 0 injection) and a post-vaccine questionnaires at Week 53 (after the Week 53 booster injection) and approximately Week 156. These questionnaires were used in the Pilot study of this MUC1 vaccine and are designed to gather information about perceived risk, regret, and symptoms. The original copies of these questionnaires will be placed in the participants’ study files. Copies should be sent electronically to: [name] [name], MSN, University of Pittsburgh; Email: [contact]. Questions should be forwarded to [name] by email or [contact].

Information from these risk assessments will only be used as supplementary data to explain for any potential confounding factors and not for any analytical purposes.

13.2 Randomization/Stratification

Participants will be randomized in a 1:1 fashion to one of two arms (MUC1 vs. placebo), using a dynamic allocation procedure called the Pocock-Simon⁴², which balances the marginal distributions of the stratifications factors across the intervention groups and has been shown to be able to accommodate a large number of factors (10-20) without difficulty⁴³. For this study we will use the following stratification factors: number of adenomous polyps removed ≥ 3 vs. < 3 and gender.

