6.8.2 Registration/Randomization

6.8.2.1 Fax to [contact] a completed Eligibility Checklist (see CRF packet) to the CPN Registration Office between 8:00 a.m. and 4:30 p.m. Central time, Monday through Friday.

6.8.2.2 Randomization: For details, see Section 13.2.

6.8.2.3 Intervention on this protocol must commence at a CPN institution under the supervision of a CPN clinician.

6.8.2.4 Intervention cannot begin prior to Registration/Randomization and must begin \leq 14 days after Registration/Randomization.

6.8.2.5 Pathology and colonoscopy reports confirming diagnoses must be sent \leq 30 days post Registration/Randomization to the CPN QAS at CPN Operations Office, [name]; or [contact], Attention CPN QAS.

6.8.2.6 Once the intervention assignment has been ascertained by the CPN Registration Office, the appropriate blinded study agent information (MUC1 vaccine or placebo/saline injection) will be communicated to the designated data manager/nurse/pharmacist at the participant's Participating Organization. The name of this contact person is to be entered in the designated space on the eligibility checklist so the Registration Office personnel have it for each participant at the time of registering/randomizing the participant. Make sure this contact person will be available at the time of the registration so he or she can receive the information from the Registration Specialist. This contact person may not be involved in assessing adverse events or any other outcome measure and should not be the same person listed on page one of the eligibility checklist form as the person completing the form. The last page of the eligibility checklist form should provide the source of communication for the contact person, either fax or email, and the appropriate contact information.

6.8.2.7 Stratification Factors:

- Number of advanced adenoma on qualifying colonoscopy: ≥ 3 vs. < 3
- Gender: male vs. female

After the participant has been registered on to the study, values of the stratification factors will be recorded. Randomization will be performed by CPN personnel. The CPN electronic-based randomization system will be utilized to ensure that randomization of participants to appropriate study arms while balancing the stratification variables is carried out successfully.

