13.4 Primary Objective, Endpoint, Analysis Plan

The primary objective for this study is to compare the ratio of the week 12 to week 0 IgG levels between the MUC1 vaccine and placebo. It is hypothesized that this ratio will be increased in patients treated with the MUC1 vaccine as compared to patients receiving the placebo. Prior data from a pilot study of 39 patients that were treated with the MUC1 vaccine³⁷ showed a mean IgG ratio of 6.46 with a standard deviation of about 10. Assuming equal standard deviations (i.e. 10) across the MUC1 and placebo groups, and assuming up to a 10% drop-out rate by year 1 (presumably less by 12 weeks), retaining at least 50 evaluable participants per arm yields at least 86% power to detect an increase in the mean IgG ratio from 1 to 6.5 for placebo vs. MUC1 (effect size = 0.55), using a 1-sided t-test with a significance level of 0.05. If the data are not normally distributed, we will use the Wilcoxon Rank-Sum test for this primary endpoint analysis. If the vaccine shows a significant increase in the 12-week immune response rate as compared to placebo, we will proceed to Part 2.

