13.5 Secondary Objectives, Endpoints, Analysis Plans

As discussed previously, there will be key powered secondary endpoints for this study across all 3 parts.

1) Immune response at 12 weeks (Part 1): The key secondary endpoint for Part 1 will compare the proportion of patients that have at least a 2-fold increase in the IgG ratio (week 12/week 0) between MUC1 and placebo. Based on the pilot study³⁷, we hypothesize that around 40% of vaccinated participants will demonstrate a 2 fold increase in MUC1 titer at week 12 compared to around 10% for the placebo arm. Assuming a drop-out rate of up to 10% by 1 year (presumably less by 12 weeks), retaining at least 50 evaluable participants per arm provides 94% power to detect an increase in the 12-week immune response rate from 10 to 40%, assuming a 2-sided significance level of 0.05 (nQuery Advisor 6.01).

2) Booster Response at 1 year (Part 2): The key secondary endpoint for Part 2 will assess the booster response at week 55 vs. week 52 for the vaccine as compared to placebo. Based on the pilot study, we expect 75% of week-12 responders will respond with a doubling of MUC1 antibody levels, or about 35% of the overall sample. We expect the 1-year response rate to be around 10% in the placebo group. Of the 110 randomized participants (55/arm), we expect that up to 10% will drop out by 1 year, leaving

approximately 100 participants evaluable for this analysis (50/arm). With 50 evaluable participants per arm, we would have 92% power to detect an increase in the 1-year immune response rate from 10 to 35%, assuming a 1-sided significance level of 0.05 (nQuery Advisor 6.01). We will also compare the actual IgG ratio values between the 2 treatment arms as well. If the booster vaccine shows a significant increase in the 1-year immune response as compared to placebo and a response rate that exceeds 15%, we can proceed to Part III.

3) Adenoma recurrence rate at 3 years (Part 3): Part 3 will evaluate the adenoma recurrence rate at least one year and up to 3 years. The adenoma recurrence rate at 3 years in participants with an adenoma is generally around 40-50%³³. Assuming an additional 10% drop out rate between years 1 and 3, we will have 90 participants (45/arm) evaluable for this endpoint, which will provide >80% power for the different effect sizes shown in the table below (1-sided alpha = 0.05).

# Evaluable	Effect Size (delta)	Power	1-sided alpha
90 (45/arm)	50 vs. 25%	79%	0.05
90 (45/arm)	45 vs. 20%	82%	0.05

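### Allocation is minimized on an adenoma count and gender, but no planned comparison uses either factor; adjusting for them would be a small, nearly free improvement

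*Combined protocol and SAP*

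**What the plan says.** Section 13.2 states "Participants will be randomized in a 1:1 fashion to one of two arms", "using a dynamic allocation procedure called the Pocock-Simon" method, which "balances the marginal distributions of the stratifications factors across the intervention groups", and gives the factors as "number of adenomous polyps removed ≥ 3 vs. < 3 and gender". Section 6.8.2.7 words the first factor differently: "Number of advanced adenoma on qualifying colonoscopy", with the same cut at three. It adds that "values of the stratification factors will be recorded", so the data needed for adjustment will exist.

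For the primary endpoint, the week 12 to week 0 IgG ratio, Section 13.4 computes power "using a 1-sided t-test with a significance level of 0.05. If the data are not normally distributed, we will use the Wilcoxon Rank-Sum test". No covariate or stratum is mentioned. Section 13.5 gives power for two-fold response, booster response and adenoma recurrence but names no test. For the booster it says "With 50 evaluable participants per arm, we would have 92% power to detect an increase in the 1-year immune response rate from 10 to 35" percent, one-sided 0.05. Sections 13.6 to 13.9 add no covariate, stratified test or re-randomization test. Section 13.10 uses two-sample t or rank-sum tests, and chi-square or Fisher tests, for the translational comparisons.

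**The concern.** Minimization removes most of the chance difference between arms on the balancing factors. An unadjusted test still counts the variation between factor levels as noise in its standard error. If the factors predict the outcome, that standard error is too large, so the test rejects a true null less often than its nominal level, has less power than it could, and gives slightly wide confidence intervals.

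Two features give this some practical weight. A significant result is the condition for moving from Part I to Part II and, together with a response-rate threshold, from Part II to Part III (Sections 13.4, 13.5 and 13.9). Part III has only 45 evaluable per arm, and one row of its power table is at 79%. There is also a specification gap: with no test named for the binary endpoints, the choice between adjusted and unadjusted results is left open.

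**Working it through.** **Inputs from the documents.** Primary: 50 per arm, difference 6.5 − 1 = 5.5, SD 10, one-sided 0.05 (Section 13.4). Binary: 50 per arm, 10% vs 40% two-sided and 10% vs 35% one-sided; 45 per arm, 50% vs 25%, 45% vs 20% and 40% vs 15% one-sided (Section 13.5).

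**Not in the documents, so assumed.** The share of outcome variance explained by the two factors (R²), their effects on recurrence, the proportion with three or more adenomas, and the minimization probability (0.8).

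**Step 1: reproduce the plan's power.** The primary standard error is 10 × √(2/50) = 2. Then 5.5/2 = 2.75, and Φ(2.75 − 1.645) = Φ(1.105) = 86.5%. The noncentral t with 98 df gives 86.1%. The plan says at least 86%.

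For proportions, power = Φ{[d − z√(2p̄(1−p̄)/n)] / √([p₁(1−p₁)+p₂(1−p₂)]/n)}. For the booster, d = 0.25, p̄ = 0.225 and n = 50, so (0.25 − 1.645 × 0.0835)/0.0797 = 1.413, or 92.1% (plan 92%). The others are 94.6% (plan 94%) and 79.8%, 82.1% and 85.4% (plan 79%, 82% and 85%). The unadjusted two-proportion formula therefore accounts for every figure.

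**Step 2: primary endpoint.** Under perfect balance the adjusted and unadjusted estimates coincide. Their true standard error is 2√(1−R²), but the unadjusted test uses 2. Its actual size is 1 − Φ(1.645/√(1−R²)); for R² = 0.10 this is 1 − Φ(1.734) = 4.2%. Adjusted power comes from the noncentral t with SD 10√(1−R²) and 96 df. The simulation used 100 participants, 20% with three or more adenomas and 50% male, with 10,000 null and 5,000 alternative runs per row.

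| Assumed R² | Unadjusted size, formula | Unadjusted size, simulated | Adjusted power, formula | Simulated power, unadjusted → adjusted |
|---|---|---|---|---|
| 0 | 5.0% | 4.9% | 86.1% | 85.8% → 85.9% |
| 0.02 | 4.8% | 4.8% | 86.7% | 86.8% → 87.2% |
| 0.05 | 4.6% | 4.7% | 87.6% | 86.4% → 87.5% |
| 0.10 | 4.2% | 4.4% | 89.1% | 87.6% → 89.5% |
| 0.20 | 3.3% | 3.8% | 92.0% | 89.6% → 92.5% |

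**Step 3: Part III recurrence**, unadjusted z-test versus Cochran-Mantel-Haenszel (CMH) test over the four factor strata.

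- 45% vs 20%, 90 participants, 25% with three or more adenomas. With no factor effect, power is 82.9% vs 82.2% and size 6.3% vs 5.4%. With odds ratios 2 (count) and 1.5 (gender), power is 84.4% vs 84.4% and size 5.8% vs 5.5%. With odds ratios 4 and 2, power is 84.1% vs 85.6% and size 4.8% vs 5.0%.
- Treatment odds ratio 0.33, matching the 50% vs 25% row since (0.25/0.75)/(0.50/0.50) = 0.33; 90 participants, 12,000 runs. Moderate factors (30% with three or more; recurrence 42% vs 70%; gender odds ratio 1.5): power 77.0% vs 78.1%, size 4.7% vs 4.7%. Strong factors (40%; 35% vs 75%; odds ratio 2): power 70.9% vs 74.5%, size 4.3% vs 5.3%.
- The same scenarios with 110 randomized and 90 retained, as the plan expects. Moderate: gains of 1.3 and 1.7 points in two separate runs, with sizes 4.9% vs 5.0% and 5.1% vs 5.5%. Strong: a gain of about 5 points, with size 4.4% vs 5.4%. In one comparison of the strong case at equal simulated size, power was 74.0% unadjusted and 73.7% stratified (approximate, because the outcome is discrete).

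**The case against.** The strongest reply is that everything depends on prognostic effects the plan never gives. That stands. A reader might infer that the factors were chosen because they predict recurrence, or that precision is certainly being lost. Neither section listing the factors gives a reason for choosing them, and at R² = 0 nothing is lost. For antibody response, Sections 2.3 and 2.4 name only circulating suppressor cells as a correlate, and these are not a balancing factor, so the primary-endpoint gain may be close to zero.

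A reader might also infer that the unadjusted tests are generally conservative and that stratifying restores the nominal level. For Part III that is not shown under moderate effects. With weak or no effects, discreteness makes the unadjusted z-test slightly liberal; in the strong case the stratified test itself runs at 5.3% to 5.4%. The equal-size comparison shows that the strong-case gain largely reflects the difference in actual size. This is expected, because balanced estimates nearly coincide and adjustment mainly corrects the standard error.

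Nor does Section 13.5 prescribe unadjusted tests for the binary endpoints. It names none; 'unadjusted' is inferred from the power formula, and a stratified analysis would not contradict the text.

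Finally, strata may be sparse: a 10% response among 50 placebo participants is about 5 responders over four strata, and the simulations above did not examine those endpoints. This is a reason to choose the method with care, and does not favour ignoring the factors.

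**Conclusion.** The mismatch between design and analysis is real but minor. The trial balances on two recorded factors and no planned comparison uses them. Under assumed effects, adjusting gains about 0 to 2 points of power for moderate factors and about 3 to 5 for strong ones, with part of the latter due to the larger actual size of the stratified test. If the factors carry no information, the cost is negligible: no loss for the primary endpoint and 0.7 points for Part III in simulation.

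The documents do not support reading this as a threat to validity or as an error in the power calculations. Each calculated power reproduces to within a point, and where prognostic factors distort the unadjusted test, they do so toward conservatism. The size rests on assumed R², odds ratios, factor prevalence and minimization probability.

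**What to change.** First reconcile the count factor between Sections 6.8.2.7 (advanced adenomas at the qualifying colonoscopy) and 13.2 (adenomatous polyps removed), and analyse by whichever was actually used at randomization.

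Then, before any unblinded analysis:

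- **Section 13.4:** include both factors in the primary model for the IgG ratio, or use the van Elteren stratified rank test where the plan would use the rank-sum test.
- **Section 13.5:** name the test for two-fold response, booster response and recurrence: CMH stratified by the two factors, or logistic regression containing both.
- Keep the unadjusted tests as sensitivity analyses.

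The cost is a few sentences in Section 13 and one clarified definition. No new data are needed, and the sample size and power statements can stay as they are.
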